5.2.3 Protocol Deviations

Protocol deviations will be identified and documented prior to database lock.

Protocol deviations will be classified as important or minor. Subjects who have experienced important protocol deviations will be excluded from per protocol analysis sets and reported in the clinical study report (CSR).

Important protocol deviations will be appropriately grouped into different categories and summarized by treatment arm.

The summary of important protocol deviations will be performed on Full Analysis Set. A list of subjects with important protocol deviations will also be provided.

5.2.4 Demographic and Other Baseline Characteristics

Demographic and baseline characteristics will be summarized for the Per-Protocol Analysis Set 1, Per-Protocol Analysis Set 2, and Full Analysis Set.

The following demographic and baseline characteristics will be summarized:

- Age (years)
- Age group (<65 years, ≥65 years)
- Gender
- Race
- Race group (White, All Others)
- Ethnicity
- Region (Eastern Europe, Western Europe, North America, Asia/Pacific)
- Height (cm)
- Baseline weight (kg)
- Baseline body mass index (BMI) (kg/m²)
- Karnofsky performance status (KPS)
- New York Heart Association (NYHA) classification
- Prior PD-1/PD-L1 treatment (Yes, No)
- MSKCC risk group (Favorable, Intermediate, and Poor risk)
- Baseline hypertension status (Yes, No)

The following disease history and characteristics at study entry will also be summarized:

- Time since the first RCC diagnosis to date of randomization (months)
- RCC diagnosis classification (predominant clear cell, other)

- Age at diagnosis (years)
- RCC American Joint Committee on Cancer (AJCC) Tumor-node-metastasis (TNM) staging at diagnosis
- Type of tumor lesions at screening (baseline):
 - Target lesions
 - Lymph node (Yes, No)
 - Non-lymph node (Yes, No)
 - Non-target lesions (Yes, No)

The following prior anticancer therapies will also be summarized:

- Number of prior therapy regimens
- Prior VEGF-targeted therapy (Yes, No)
- Prior biological agents (Yes, No)
- Duration of last therapy (months)
- Best response for last anticancer therapy (complete response (CR), partial response (PR), stable disease (SD), progressive disease (PD), not evaluable (NE), not applicable (NA), unknown)
- Time from end of last therapy to date of randomization (months)
- Prior treatment regimen (adjuvant, locally advanced, metastatic, neoadjuvant, unknown)
- Prior radiotherapy (Yes, No)
 - Time from last radiotherapy to date of randomization (months)
 - Site of prior radiotherapy
 - Tumor lesion at the site progressed since last radiotherapy (Yes, No, Not evaluated)
- Prior VEGF-targeted therapy
 - Duration of most recent VEGF-targeted therapy (months)
 - Best response for most recent VEGF-targeted therapy
 - Time from end of most recent VEGF-targeted therapy to date of randomization (months)
 - Type of prior VEGF-targeted therapy (adjuvant, locally advanced, metastatic, neoadjuvant, unknown)

In addition, a summary of stratification factors used in the randomization (MSKCC prognostic group and prior PD-1/PD-L1 treatment) based on IxRS data will be provided to evaluate whether or not randomization process was appropriately executed in the study.

Demographic and baseline disease characteristics, prior anticancer therapies will also be listed for each subject.

MEDICAL HISTORY

General medical history will be coded using the Medical Dictionary for Regulatory Activities (MedDRA) Version 22.1 or higher and summarized by body system organ class (SOC) and preferred term (PT) for each treatment group and overall.

A subject data listing of medical history will be provided, including SOC and/or PT, current medical condition, date of diagnosis or surgical procedure or onset of symptoms, and end date/on-going.

5.2.5 Prior and Concomitant Therapy

All investigator terms for medications recorded on the case report form (CRF) will be coded using the World Health Organization Drug Dictionary (WHO DD) Version of March 2018 or later.

Prior medications will be defined as the medications that were started prior to the first dose of study drug. Concomitant medications will be defined as the medications that (i) started before the first dose of study drug and were continuing at the time of the first dose of study drug, or (ii) started on or after the date of the first dose of study drug up to 28 days following the last dose in randomization phase. Medications that cannot be determined to be prior/concomitant/posttreatment due to missing or incomplete dates will be regarded as concomitant.

Prior medications will be summarized by anatomical class (Anatomical Therapeutic Chemical [ATC] Level 1), pharmacologic class (ATC Level 3), and WHO DD preferred term. A similar summary will also be provided for concomitant medications except thyroxine suppression therapy and antihypertensive therapy. Concomitant thyroxine suppression therapy and antihypertensive therapy will be summarized separately. In addition, a separate summary for the concomitant medications of P-glycoprotein inhibitors and/or inducers will be provided.

Data listings will be generated for all prior and concomitant medications, concomitant thyroxine suppression therapy, concomitant antihypertensive therapy, and concomitant P-glycoprotein inhibitors and/or inducers.

Prior and concomitant medications/therapies will be summarized for Per-Protocol Analysis Set 1 and Full Analysis Set.

5.2.6 New Anticancer Therapies

The total number of subjects who received new anticancer therapies during Follow-up period will be reported for Per-Protocol Analysis Set 1 and Full Analysis Set in each treatment group. A summary of new anticancer therapy will be presented by anatomical class (ATC Level 1), pharmacologic class (ATC Level 3), and WHO DD preferred term. The number of anticancer regimens received, the duration of the first new anticancer regimen, and the primary reason for discontinuation of the first new anticancer regimen will also be summarized.

The new anticancer procedures during Follow-up period will also be reported.

5.2.7 Treatment Compliance

Records of treatment compliance for each subject will be kept during the study, including the Follow-up Period. Clinical research associates will review treatment compliance during investigational site visits and at the completion of the study. Received dose as percent of planned dose per subject (ie, relative dose intensity) will be summarized as described in [Section 5.6.2.2](#), no other analysis of treatment compliance is planned.

5.3 Data Analysis General Considerations

5.3.1 Pooling of Centers

Subjects from all centers will be pooled for analyses. For the subgroup analysis for region, subjects from all centers within each region will be pooled for the analysis.

5.3.2 Adjustments for Covariates

For the analyses of primary efficacy endpoint of ORR_{24W} and primary safety endpoint of proportion of subjects with intolerable Grade 2 or any \geq Grade 3 TEAEs within 24 weeks after randomization, the CMH test stratified by the randomization stratification factors of MSKCC prognostic group and prior PD-1/PD-L1 treatment will be used.

The stratified analyses will be performed using the stratification factors from IxRS data. For the stratification factor of MSKCC prognostic group from IxRS, some subjects with MSKCC Prognostic Score 2 were misclassified to intermediate risk on IRT system which should have been classified to poor risk per protocol. The poor risk group will be pooled with the intermediate risk group in the relevant stratified analyses based on IxRS data, the favorable risk group will remain intact. The analyses based on the stratification factors from CRF data in clinical database may also be performed as sensitivity analyses.

To explore homogeneity of treatment effect across centers/regions, sensitivity analyses will be conducted to adjust center/region effect for the primary endpoints of ORR_{24W} and the proportion of subjects with intolerable Grade 2 or any \geq Grade 3 TEAEs within 24 weeks after

randomization using logistic regression models including center/region and stratification factors as covariates.

Other demographic and baseline variables may be included and adjusted in the statistical models as sensitivity analyses if deemed necessary.

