6 INVESTIGATORS AND STUDY PERSONNEL

[figure not shown]
This study will be conducted by qualified investigators under the sponsorship of Eisai (the sponsor) at approximately 100 investigational site(s) worldwide.

The name and telephone and fax numbers of the medical monitor and other contact personnel at the sponsor and of the contract research organizations (CROs) are listed in the Investigator Study File provided to each site.

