To explore homogeneity of treatment effect across centers/regions, sensitivity analyses will be conducted to adjust center/region effect for the primary endpoints of ORR_{24W} and proportion of subjects with intolerable Grade 2 and any \geq Grade 3 TEAEs within 24 weeks after randomization using logistic regression models, including center/region as a covariate.

Determination of whether 14 mg lenvatinib can be used as an alternative dosing strategy will be based on clinical judgment by the sponsor in consultation with the independent DMC (as specified in the DMC charter) by assessing risks and benefits according to the totality of the safety and efficacy data.

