5.3.4 Examination of Subgroups

In general, subgroup analyses on the prespecified subgroups in Table 4 will be performed for the efficacy endpoint ORR based on the investigator assessment and the primary safety endpoint of proportion of subjects with intolerable Grade 2 or any \geq Grade 3 TEAEs within 24 weeks after randomization.

Exploratory analysis on the subgroup of subjects previously treated with PD-1/PD-1 will be performed and is specified in the [Section 5.8.2](#).

Additional subgroup analyses may be performed as appropriate.

Table 4: Subgroup Analyses for Efficacy and Safety Endpoints

Subgroup	Definition
Sex	Male, Female
Age	<65, ≥ 65 years

Race	White, Non-White
Region	Eastern Europe, Western Europe, North America, Asia/Pacific
Baseline hypertension status	Yes, No
MSKCC risk group	Favorable, Intermediate, and Poor risk
Prior PD-1/PD-L1 treatment	Yes, No

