The treatment difference in ORR_{24W} between lenvatinib 14 mg and lenvatinib 18 mg will also be estimated along with 90% CIs based on the asymptotic normal approximation.

If non-inferiority in ORR_{24W} is claimed, the superiority test at 2-sided $\alpha=0.05$ for the primary safety endpoint will be performed. The details are specified in Primary Safety Endpoint [Section](#)

5.6.1.

Sensitivity analyses of ORR_{24W} based on Full Analysis Set and Per-Protocol Analysis Set 2 will be performed in a similar manner as described above.

To explore homogeneity of treatment effect across centers/regions, a sensitivity analysis of ORR_{24W} using logistic regression model with center/region along with stratification factors as covariates will be conducted to adjust center/region effect.

Sensitivity analyses of ORR_{24W} based on the stratification factors from CRF data in clinical database will also be performed on Per-Protocol Analysis Set 1, Full Analysis Set and Per-Protocol Analysis Set 2.

For this study, for subjects in the lenvatinib 14 mg QD with everolimus 5 mg arm, lenvatinib dose should be escalated to 18 mg QD (with everolimus 5 mg) as long as there are no intolerable Grade 2 or any \geq Grade 3 TEAEs that require dose reductions in the first 28-day cycle. To evaluate any potential impact due to failing to up-titrate the doses for eligible subjects in the lenvatinib 14 mg QD with everolimus 5 mg arm, another sensitivity analysis may be performed on Per-Protocol Analysis Set 1 to exclude those subjects who should have been up-titrated by protocol but were actually not up-titrated by investigators, if the number of such cases in the lenvatinib 14 mg QD with everolimus 5 mg arm is deemed high (eg, $\geq 10\%$).

An analysis of ORR_{24W} based on the data prior to when the protocol was amended to open-label (from double-blinded) (ie, treatment assignments were unblinded to investigator sites on 14 July 2018) will be performed on Per-Protocol Analysis Set 1 and Per-Protocol Analysis Set 2 to check for consistency of study results before and after the protocol became un-blinded.

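### The center/region model meant to explore homogeneity has no treatment interaction, so it cannot show heterogeneity, and no region-specific ORR24W result is committed

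*SAP*

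**What the plan says.** SAP 5.3.2 gives the aim and scope: "To explore homogeneity of treatment effect across centers/regions, sensitivity analyses will be conducted to adjust center/region effect for the primary endpoints". The two endpoints concerned are ORR24W and the primary safety endpoint. The method in the same section is "randomization using logistic regression models including center/region and stratification factors as covariates".

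SAP 5.4.1 repeats this for ORR24W, "using logistic regression model with center/region along with stratification factors as covariates will be conducted to adjust center/region effect", and SAP 5.6.1 says the same for the primary safety endpoint. The protocol version (9.7.1.6.1 and synopsis) is "using logistic regression models, including center/region as a covariate". None of these places has a treatment-by-center or treatment-by-region term, and none says whether center or region will be used.

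The plan looks at region separately. SAP Table 4 lists four regions (Eastern Europe, Western Europe, North America, Asia/Pacific). Under SAP 5.3.4 the Table 4 subgroup work "will be performed for the efficacy endpoint ORR based on the investigator assessment" and for the primary safety endpoint. SAP 5.4.4 adds forest plots and gives homogeneity across subgroups as their purpose. ORR24W is not on that list, and further subgroup analyses are optional.

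Protocol section 6 plans the trial "at approximately 100 investigational site(s) worldwide". SAP 5.3.1 pools all centers for analysis. It gives no rule for combining small centers in this model, and no conditional, random-effect or penalized fit is named.

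**The concern.** The stated question is whether the treatment effect differs between places. The planned model answers another one: what the common treatment effect is after allowing for different baseline rates between places. A reader of the study report could take an adjusted odds ratio close to the primary one as evidence of homogeneity, which it is not.

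Regional or site differences are plausible here. Response is investigator-assessed, intolerability of a Grade 2 event is a matter of subject or physician judgment, and sites have been unblinded since 14 Jul 2018.

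The unresolved wording adds a second risk. If center is chosen and fitted as ordinary fixed effects, sparse data push the odds ratio away from 1. The sensitivity result could then look discordant with the primary result, or exaggerate a benefit, for purely technical reasons.

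**Working it through.** **Inputs.** PPAS1 of 306 subjects, 153 per arm; ORR24W 37% (18 mg) and 45% (14 mg); margin 0.76 on the odds ratio (SAP 4). Safety rate 75% with a 15-point drop to 60% (SAP 4). About 100 sites (Protocol 6). Four regions (SAP Table 4). Randomization is not stratified by site (SAP 3.2). Site sizes are not given, so they are assumed below.

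**Plan's own figures.** Design odds ratio = (0.45/0.55)/(0.37/0.63) = 1.393. Fixed-design size per arm = (1.645 + 0.842)² × [1/(0.37×0.63) + 1/(0.45×0.55)] / (ln 1.393 − ln 0.76)² = 6.18 × 8.33 / 0.367 ≈ 140.3, so 141. With the three looks and stated boundaries, 153 per arm gives 80.1% power when futility is acted on, with one-sided alpha 0.0499. The safety comparison has 80.3% power, at an odds ratio of (0.60/0.40)/(0.75/0.25) = 0.50. The design reproduces.

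**Step 1: what the planned model can return.** For a subject in region r with treatment indicator T and stratification factors Z, the plan fits

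logit P(Y=1) = α_r + βT + γZ.

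The treatment odds ratio is exp(β) in every region by construction. To let it vary, the model must be

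logit P(Y=1) = α_r + (β + θ_r)T + γZ,

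with region-specific odds ratio exp(β + θ_r) and a 3-df test that all θ_r are equal.

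Illustration with four equally likely regions and log odds ratios 1.2, 0.9, −0.4 and −0.4 (odds ratios 3.32, 2.46, 0.67, 0.67). The simple average is 1.3/4 = 0.325, and exp(0.325) = 1.38. Over 400 simulated trials the main-effect model gave a median of 1.43, close to the design value, with nothing to show that two regions point the other way. The interaction test gave P < 0.10 in 84% of these trials.

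**Step 2: center against region.** Average site size is 306/100 = 3.06. Each setting used 2,000 simulated trials and maximum-likelihood logistic regression with treatment and place indicators. The stratification factors were left out for simplicity. Entries are median estimated odds ratios.

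| Place factor and assumed site sizes | True 1.393 | True 0.76 | True 0.50 (safety) |
|---|---|---|---|
| 4 regions | 1.41 | 0.75 | 0.50 |
| 100 centers, equal expected size | 1.58 | 0.70 | 0.39 |
| 100 centers, skewed (gamma shape 1.0) | 1.51 | 0.72 | 0.44 |
| 100 centers, more skewed (gamma shape 0.5) | 1.48 | 0.73 | not run |

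At a true 1.393 with 100 centers, the mean log odds ratio is 1.20 to 1.40 times the true value. The empirical SD is 0.31 to 0.39 against a mean model SE of 0.28 to 0.33, so the SE is understated. Sites with all or no responders carry no information, leaving about 38 to 60 sites and 234 to 266 subjects. A Mantel-Haenszel odds ratio stratified by center has a median of 1.40 in the same data.

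Repeat simulations under other site-size assumptions widen the ranges to about 1.46 to 1.62 for a true 1.39 (1.62 with exactly equal sites) and about 0.66 to 0.74 for a true 0.76.

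**Step 3: what an interaction test could find.** With milder heterogeneity (odds ratios 2.0, 1.39, 1.39, 0.9), P < 0.10 occurred in about 26% of simulated trials, against about 12% with none.

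**The case against.** The best defense is that homogeneity is examined elsewhere. The region forest plots cover the primary safety endpoint itself, for a declared homogeneity purpose, and they cover ORR, which shares with ORR24W the investigator RECIST 1.1 assessment, the confirmation rule and the 28-day and new-therapy limits. This stands in good part. A reader might infer that neither primary endpoint gets any regional look. The documents do not support that: safety does, and only region-specific model estimates and an interaction test are missing there. For efficacy the gap is narrow but real, because ORR runs to data cutoff and ORR24W by region is only optional.

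Second, the plan never says that about 100 center indicators will be fitted by unconditional maximum likelihood. A reader might infer that the planned analysis will distort the odds ratio. It would do so only under the center reading.

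Third, the Protocol's Amendment 01 history says the analysis was added in response to a regulatory question. A reader might infer that the regulator's request goes unanswered. The question itself is not in the documents, so that cannot be judged. What can be judged is the mismatch with the plan's own stated aim.

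Fourth, an interaction test is weak at this size. That is correct, and the 84% above needs a strong reversal of effect. The main gain is the region-specific estimates and their intervals, with the P value secondary.

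**Conclusion.** The point holds in a limited form. The model in SAP 5.3.2, 5.4.1 and 5.6.1 cannot serve its stated purpose, because it imposes one common odds ratio. This follows from the form of the model and needs no assumption. The remaining gap is a committed region-specific result for ORR24W, plus region-specific odds ratios and an interaction estimate for both primary endpoints.

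The distortion is conditional on center being fitted as fixed effects. Its direction is away from 1. Its size (about 1.46 to 1.62 for a true 1.39; about 0.66 to 0.74 for a true 0.76) depends on site sizes that the documents do not give.

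Nor is the trial's conclusion at risk. These are sensitivity analyses, and the primary CMH tests, stopping boundaries and N = 306 are untouched. At a true 0.76 the center model pulls the estimate further below the margin, and simulated false non-inferiority claims from it stayed at about 4% to 5%.

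**What to change.** In SAP 5.3.2, 5.4.1 and 5.6.1, replace center/region with region, at the four Table 4 levels. Keep the adjusted main-effect model if wanted, but describe it as adjustment only. For homogeneity, add a treatment-by-region term and report region-specific odds ratios with confidence intervals and a descriptive interaction P value, for ORR24W and for the primary safety endpoint.

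In SAP 5.3.4 and 5.4.4, run the Table 4 forest plots on ORR24W as well as ORR.

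Do not fit center as unconditional fixed effects. If a center-adjusted result is wanted, name a center-stratified Mantel-Haenszel, conditional logistic or random-effect method.

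The cost is one model term, one wording change and one extra set of plots, with no new data. The drawback is low power for modest heterogeneity, so the text should say in advance that the interaction result is descriptive and that a non-significant P value is not evidence of homogeneity.

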5.3.3 Multiple Comparisons/Multiplicity

There will be two interim analyses and one final analysis for the non-inferiority test on the primary efficacy endpoint ORR_{24W}. O'Brien-Fleming efficacy boundary is used to control the overall Type I error rate at the nominal level ($\alpha=0.05$ one-sided). Specifically, if the 1-sided P value is ≤ 0.005 at the first interim analysis, or ≤ 0.014 at the second interim analysis, or ≤ 0.045 at the final analysis, non-inferiority in ORR_{24W} will be claimed.

A non-binding futility will be also carried out at each interim analysis. If the 1-sided P value is ≥ 0.776 at the first interim analysis, or ≥ 0.207 at the second interim analysis, futility will be claimed.

These stopping boundaries are based on the plan that the two interim analyses will take place when the total number of 150 subjects and 200 subjects in the Per-protocol Analysis Set 1 have completed 24 weeks of follow-up or discontinued early.

Superiority on the primary safety endpoint will be tested at 2-sided $\alpha=0.05$ only if the non-inferiority on the primary efficacy endpoint ORR_{24W} is claimed.

All secondary efficacy endpoints will be analyzed descriptively, no formal statistical hypothesis tests will be performed on the secondary efficacy endpoints.

5.3.4 Examination of Subgroups

In general, subgroup analyses on the prespecified subgroups in Table 4 will be performed for the efficacy endpoint ORR based on the investigator assessment and the primary safety endpoint of proportion of subjects with intolerable Grade 2 or any \geq Grade 3 TEAEs within 24 weeks after randomization.

Exploratory analysis on the subgroup of subjects previously treated with PD-1/PD-1 will be performed and is specified in the [Section 5.8.2](#).

Additional subgroup analyses may be performed as appropriate.

Table 4: Subgroup Analyses for Efficacy and Safety Endpoints

Subgroup	Definition
Sex	Male, Female
Age	<65, ≥ 65 years

Race	White, Non-White
Region	Eastern Europe, Western Europe, North America, Asia/Pacific
Baseline hypertension status	Yes, No
MSKCC risk group	Favorable, Intermediate, and Poor risk
Prior PD-1/PD-L1 treatment	Yes, No

5.3.5 Handling of Missing Data, Dropouts, and Outliers

For efficacy endpoints related to ORR which summarize the percentage of responders, missing responses will not be imputed and subjects with missing responses will be considered as non-responders.

For incomplete dates involving efficacy and safety data such as adverse events, concomitant medications, laboratory assessments, vital signs, and echocardiogram/multigated acquisition (MUGA) data, a conservative imputation will be used for calculation if needed. The imputation rules will be specified in study analysis dataset specification with more details.

HRQoL analysis will follow FDA and EMEA PRO guidelines. Handling of missing values for HRQoL analysis will be specified in details in a separate SAP and HRQoL report.

